13.3. Withdrawal Procedures

If the decision to withdraw a subject occurs at a study visit, regular clinic visit procedures will be conducted as well as the additional termination procedures described in 13.4. If it is determined via a phone call that withdrawal is appropriate or if the subject is dropping out, we will ask the subject to attend an exit visit to return study product and equipment, complete questionnaires, product accountability and safety assessments and to receive their final study payment.

If the subject refuses an exit visit, we will request that at the minimum, study investigational product be returned and product accountability be completed. We will also stress the importance of being able to assess safety measures for the subject's safety.

13.4. Procedures for Early Termination Visits

If a Phase 2 and 3 subject decides to withdraw from the study prior to completion or if they are withdrawn by the PI/LMP due to safety concerns, they will be scheduled for an early termination visit. If the participant is seen within the window of a regularly scheduled visit, all measures for that visit will be collected. If the early termination visit occurs at Weeks 1, 2, 3, 6, or 10, additional questionnaires and safety measures will be obtained (urine sample for biomarkers and pregnancy screen, CES-D and BDI-II if appropriate) since these measures are not scheduled at those visits. If the subject is seen outside of a regularly scheduled visit window, the following measures will be obtained.

A. Physiological Measures at Early Termination:

- 1) Expired breath CO level.
- 2) Vitals signs (blood pressure, heart rate).
- 3) Weight.
- 4) First morning void, (or if missing collect a spot urine) for biomarkers analysis.
- 5) Spot urine for pregnancy tests [hCG detection] for females (first morning void used at telehealth visits).
- 6) Spot urine sample for compliance testing (first morning void used at telehealth visits).

B. Questionnaires and Assessments at Early Termination:

The following additional assessments will be completed by all early termination participants, if not part of the usual measures scheduled for the regularly scheduled visit:

- 1) Cigarette & Product Evaluation Scale – (Study Cigarettes and Usual Brand CES/PES)
- 2) CES-D:
Beck Depression Inventory 2nd Edition (BD-II) will be administered on paper if the CES-D score is 16 or greater or if monitored for psychiatric illness.
- 3) Cigarette Dependence Measures (Study Cigarettes).
- 4) Vaping/Product Dependence Scale.
- 5) Environmental Tobacco Smoke Exposure Questionnaire.
- 6) Dietary Intake.
- 7) NIAAA Alcohol Use Questionnaire (1 month).

- 8) Perceived Health Risk of no tobacco use, usual brand cigarettes, study cigarettes, smokeless tobacco, medicinal nicotine and ENDS).
- 9) Cigarette/Product Purchase Task.
- 10) End of Study Questionnaire.

B.2 Administered as an interview by the study Research Assistant (entered into REDCap):

- 1) Health Changes Questionnaire.
- 2) Adverse Events.
- 3) Concomitant Medications.
- 4) Review of Daily Call and follow-up on missing and unusual reports.
- 5) Timeline Follow Back Questionnaire (since last visit).
- 6) Recreational Drug Use Questionnaire (1 month version).
- 7) Drug accountability: Complete study Product Dispensing Log.
- 8) End of Visit Questionnaire.

The data collected during the termination visit will be used as appropriate given the days outside of visit window, subject use of study product, measures of safety or other considerations to be determined in the data analysis.

14. Risks to Subjects

14.1. Study Related Risk

Potential risks of participation are minimal and include the following:

- 1) **Survey Questionnaires:** The interviews will include questions about medical history, drug and alcohol use, and questionnaires about mood. Answering these personal questions could make the subject feel uncomfortable.
- 2) **Breach of Confidentiality:** The risk of the interview is loss of privacy if other people find out the results from individual subjects.
- 3) **Drug Testing:** A breach of confidentiality could occur and other people could learn of the subject's drug use. (Discontinued since conversion to telehealth visits.)
- 4) **Obtaining blood pressure:** The blood pressure cuff may cause minimal discomfort. In obtaining blood pressure, researchers may find out the subject has abnormal blood pressure and must refer them to their primary care physician.
- 5) **Smoking Cigarettes:** All cigarettes are detrimental to a person's health and can lead to severe or fatal medical problems including:
 - a. **Cardiovascular Diseases:** Coronary heart disease, heart attack, stroke, peripheral vascular disease, reduced blood circulation, abdominal aortic aneurysm

- b. Respiratory Diseases: Emphysema, bronchitis, tuberculosis and chronic airway obstruction
- c. Cancers: Lung, bladder, liver, colon, cervical, esophageal, kidney, larynx, mouth, pancreatic, throat, stomach cancers and acute myeloid leukemia
- d. Diabetes
- e. Immune function, rheumatoid arthritis
- f. Other Health Risks Associated with Smoking: Including but not limited to infertility, ectopic pregnancy, miscarriage, lower bone density in postmenopausal women, hip fracture in women, male sexual dysfunction; age-related macular degeneration, blindness and cataracts

6) Smoking VLNC Study Cigarettes (NNC are similar to commercial cigarettes): In addition to the above medical problems, subjects may experience some minor adverse health effects such as headaches or experience withdrawal symptoms, which are listed below. Due to the altered nicotine levels, there could be a change in their cigarette use including the manner in which they inhale the smoke or increase in the number of cigarettes smoked per day. This increased rate of smoking may persist after completing the study. Smoking the study cigarettes does not provide any less risk than their usual brand cigarette and could pose increased health risks. Participants may also experience increases in levels of carbon monoxide, a gas from smoke. The study cigarettes are made from genetically modified tobacco plants. A recent toxicological analysis of these cigarettes showed that the concentrations of many harmful tobacco constituents, including polycyclic aromatic hydrocarbons, ammonia, and toxic metals, were similar to the concentrations of these constituents in commercial cigarettes ⁶⁰.

7) ENDS: ENDS can expose users to several chemicals, including nicotine, carbonyl compounds, and volatile organic compounds, known to have adverse health effects. The health effects and potentially harmful doses of heated and aerosolized constituents of ENDS liquids, including solvents, flavorants, and toxicants, are not completely understood. ENDS aerosol is not harmless although it generally contains fewer toxicants and at lower levels than combustible tobacco products. Specific potential known risks include:

- a. ENDS contain nicotine, which may contribute to some of the disease associated with smoking.
- b. The most common side effects related to ENDS use are changes in taste, mucus in throat/sinus, dry mouth, dry cough, throat irritation, sore throat, mouth ulcers, dizziness, headache, and nausea.
- c. While uncommon, the batteries from ENDS have exploded/ignited and injured users.
- d. ENDS can overheat and present a minor burn risk if the button is turned on repeatedly. Subjects are told to be careful if storing the device in a place where the button might be accidentally pressed often. In rare cases the cartridge or pod containing the e-liquid has cracked or leaked e-liquid. Refilling of the tanks may also result in e-liquid spills. Subjects are instructed to immediately wash any exposed skin with soap and water.

- e. Ingestion of ENDS liquids containing nicotine can cause acute toxicity and possible death if the contents of refill cartridges containing nicotine are consumed. Subjects are told to keep study ENDS and all e-liquid cartomizers away from pets and children.
- f. Nicotine is an addictive chemical. It is possible that this experience could lead to long-term use of ENDS after the trial is over.
- g. Allergic reactions to propylene glycol, vegetable glycerin or flavorants have been reported. If a subject reports a medical history of these allergies after randomization they will not be offered the vaping products in the marketplace. Chemicals used to flavor foods are also a risk for allergic reactions. We will ask subjects if they have had allergic reactions to specific nuts, fruits, and other flavors and advise them not to use e-liquids/cartridges that may contain or be labeled with those flavors.
- h. Recent reports of seizure associated with vaping are being evaluated by the CDC and the FDA. While collection of evidence for seizure is not conclusive of causality, it is prudent to inform potential subjects of this investigation.
- i. Reports of severe lung disease and deaths are being investigated by the CDC and the FDA. These incidents have been predominantly attributed to vaping THC and vitamin E acetate. Participants will be alerted to the symptoms of lung disease including: cough, shortness of breath, chest pain, nausea, vomiting, abdominal pain, fever. Participants are advised to discontinue use and promptly seek medical attention for any health concerns. Participants will also be advised to use only the study product we have provided to them and to not alter the device or add any substances to e-fluids. We will keep the participants informed as the additional information is provided by the CDC and FDA.

8) Use of Smokeless Tobacco or Snus: Smokeless tobacco products could increase risk for mouth sores, gum disease and tooth loss, nausea or upset stomach, vomiting, high blood pressure and nicotine addiction. Smokeless tobacco products may increase the risk of cancer, particularly oral, esophageal and pancreatic cancer. However, these risks are less than the health risks of smoking combustible cigarettes.

9) Use of Medicinal Nicotine (nicotine polacrilex and transdermal patch) or nicotine pouches: Most common adverse effects for medicinal nicotine include irregular heartbeat/palpitations, high blood pressure, mouth sores, mouth or throat irritation, heartburn, upset stomach, vomiting, diarrhea, dizzy or lightheadedness, and hiccups or belching. Additional adverse effects associated with nicotine gum include teeth or jaw problems. Additional adverse effects associated with nicotine patch are erythema, pruritus, edema and sleep disturbance. There may also be a risk of nicotine toxicity including symptoms such as nausea, dizziness, vomiting, diarrhea, and weakness.

10) Dual use of tobacco or nicotine products: There is also the chance of use of more than one product that may result in symptoms of nicotine toxicity and/or continued use of the products. However, cessation of all tobacco products will be strongly recommended to the subjects both at the end of the experimental phase and at follow-up with referrals to local cessation treatments or state quit line.

11) Smoking Withdrawal: Participants may experience smoking withdrawal symptoms during this study. The symptoms can be uncomfortable but are typically of minimal risk. Smoking withdrawal symptoms include:

- a. Anger, irritability, frustration
- b. Anxiousness, nervousness
- c. Depressed mood or sadness
- d. Desire or craving to smoke
- e. Difficulty concentrating
- f. Increased appetite, hunger or weight gain
- g. Insomnia, problems sleeping or awakening at night
- h. Restlessness
- i. Impatience
- j. Constipation
- k. Dizziness
- l. Coughing
- m. Dreaming or nightmares
- n. Nausea
- o. Sore Throat

12) Returning to Regular Smoking: It is possible that if participants return to smoking their usual brand of cigarette at the end of the study they may experience mild and transient nausea, dizziness, and lightheadedness.

13) Changes in Blood Pressure and/or Heart Rate: Smoking and nicotine can affect the cardiovascular system, which may result in changes in blood pressure and/or heart rate.

14) Changes in Mood, Emotions and Psychiatric Symptoms: Smoking and nicotine can affect a person's mood and emotions and are associated with psychiatric disorders including major depressive disorder, general anxiety disorder, bipolar disorder and eating disorders. Any changes in nicotine use or cigarette consumption could adversely affect mood, emotions and the symptoms related to psychiatric conditions in some individuals.

15) Smoking and Oral Contraceptives in Women: Women who smoke and are over the age of 35 should not take oral contraceptives that contain estrogen without consulting their physician. Smoking while using oral contraceptives can increase the risk of having a cardiovascular event such as a heart attack or stroke. Additionally, there is a potential risk of thrombosis associated with hormonal therapy (including contraceptives) and smoking.

16) Smoking and Medications: Quitting smoking can greatly benefit participants' health. However, changes in smoking can lead to changes in how well some medications work. Participants are asked to disclose all medications they are taking. We also recommend that participants discuss any planned or actual changes in how much they smoke with their doctor, especially if they are taking any medications for psychiatric, cardiovascular, or other serious diseases.

14.2. Reproductive Risks

Risk to Fetus: Smoking during pregnancy can lead to miscarriage, preterm delivery, stillbirth, low birth weight, problems with the placenta, birth defects such as cleft palate, sudden infant death syndrome (SIDS), and early childhood behavioral problems. Smokeless tobacco/snus/nicotine pouches use increases risks for preterm delivery, preeclampsia or stillbirth and may have a negative effect on birth weight. Although unknown, similar effects could occur with the use of ENDS.

Avoiding Risks to Fetus

If female participants choose to be sexually active, they are asked to use an appropriate “double barrier” method of birth control (such as female use of a diaphragm, intrauterine device (IUD), or contraceptive sponge in addition to male use of a condom), or should be using prescribed “birth control” pills, injections, or implants. Female participants with child-bearing potential will be tested for pregnancy at the first Marketplace visit and the randomization visit and monthly thereafter. If a participant becomes pregnant during the study, she will be withdrawn from the study if using tobacco or ENDS products. Approximately 30 days after being withdrawn or having a positive pregnancy test, the research staff will call the participant to confirm her due date. The licensed medical professional will follow-up with the participant after delivery to ask questions about the baby’s health.

14.3. Risks to Others

Tobacco products in the home can be toxic to children and pets. Smoking can lead to second hand exposure that can increase risk for disease. All participants will be informed to keep products not accessible to children and pets and informed about the harms of second hand smoke and vapor exposures in the home or in cars.

15. Potential Benefits of Participation

There are no immediate benefits from participating in the study.

The information obtained from this study may ultimately help the Food and Drug Administration decide how best to regulate tobacco products with the goal of improving public health.

16. Data Management

16.1. Data analysis plan

For complete statistical detail, please see Statistical Analysis Plan.

16.2. Randomization

Subjects will be randomized at the end of Phase 2 with a 1:1 ratio to the two studied conditions described above. Randomization will be stratified by site (6 study sites) using a blocked

randomization scheme with random block sizes of 2, 4, and 6. We anticipate no or less than minimal block effects in our data based on previous studies with similar design.

16.3. Sample Size

We will enroll 400-450 subjects (approximately 200-225 per group) to the study and assume a 20% attrition rate over the 12-week post randomization period. Power analysis was performed for two of the primary outcomes in the primary aim: CPD smoked at the end of Phase 3 and smoke-free days during Phase 3. The effect sizes and the distribution of population demographics were projected from a pilot study (U19CA157345; Hatsukami et al., 2017) and Donny et al. (2015)^{16,14}. The two-sided type-I error rate for each outcome (CPD and smoke-free days) was set at $\alpha=0.025$ ($=0.05/2$ outcomes by the Bonferroni method) for the overall sample. Powers for two independent subgroup analyses, by sex or by age, are also presented in Table 1, with type I error rate equal to α divided by the number of subgroups ($=2$) for each factor. T-test was used for the CPD outcome. For the smoke-free days outcome, we first calculated the rate of smoke-free days by dividing the number of smoke-free days by the total number of days in Phase 3 (approximately 84 days) and then used z-test for the Poisson rate difference. PASS 13 was used for power calculations.

Table 1: Power Analysis for Total Enrolled (randomized) N=450 and 400

Primary outcomes	VLNC	NNC	Overall sample	³ Subgroup analysis by sex		⁴ Subgroup analysis by age		
				F	M	18-24	25-44	45+
N enrolled = 450								
¹ Cigarettes (study or non-study) per day smoked at the end of Phase 3 (calculated as mean CPD based on 7 days' IVR data before the week 12 visit)	7	15	>.99	>.99	>.99	-	>.99	>.99
² Number of smoke-free days during Phase 3 (12 weeks or 84 days)	11 days difference		.92	.49	.56	-	.67	.37
N enrolled = 400								
¹ Cigarettes (study or non-study) per day smoked at the end of Phase 3 (calculated as mean CPD based on 7 days' IVR data before the week 12 visit)	Same as above		>.99	>.99	>.99	-	>.99	>.99
² Number of smoke-free days during Phase 3 (12 weeks or 84 days)			.88	.43	.50	-	.61	.32

¹We assumed an equal SD for the two treatment arms. See Table 1 (left panel) in SAP for SD for the overall group, by gender and by age.

² The NNC arm's rate of abstinence was based on the interim analysis result (see Table 1 in SAP, right panel).

³44.7% female and 55.3% male, based on the interim data (see Table 1 in SAP).

⁴0.2%, 53.4%, and 44.7% for 18-24, 25-44, and \geq 45 years old, respectively, based on the interim data (see Table 1 in SAP).

16.4. Study Populations

16.4.1. Intent-to-Treat

The primary analysis of all endpoints will adhere to the intent-to-treat principle. Under this principle, all randomized subjects will be included in the analysis in the group to which they were randomized regardless of protocol violations and compliance to treatment assignment.

16.4.2. Definition of Sub-Group Population in Different Analyses

We intend to complete pre-planned subgroup analyses by sex, age groups (18-44, and 45+), and whether the participant was recruited pre- or post-COVID. Subgroup analysis will allow us to evaluate the consistency of the effect of VLNC vs. NNC across important subgroups.

16.5. Trial Endpoints

16.5.1. Primary Endpoints

- Cigarettes per day (CPD): the mean cigarettes (study and non-study cigarettes) smoked per day based on 7 days' Daily Interactive Voice Response (IVR)-Revised data before the week 12 visit.
- Smoke-free days: the number of smoke-free days during Phase 3, based on IVR-Revised during Phase 3.

16.5.2. Secondary Endpoints

- Biomarker: percent change in biomarker, CEMA, at the weeks 4, 8 and 12 visits during Phase 3 as compared to the last visit in Phase 2.
- Study Cigarettes per day (CPD): the mean study cigarettes smoked per day based on 7 days' Daily Interactive Voice Response (IVR)-Revised data before the week 12 visit.
- Smoke-free point prevalence: Smoke-free days based on IVR-Revised and biochemical verification of smoke-free status ($CO \leq 6\text{ppm}$) 7 days prior to the end of the 12 week.

16.5.3. Exploratory Endpoint

- Non-combusted tobacco/nicotine products use: the number of days using any non-combusted tobacco/nicotine products in Phase 3.
- Characteristics of products chosen (type, flavor, nicotine strength).

- Biomarkers: percent change in other biomarkers (Total Nicotine Equivalents, total NNAL, other mercapturic acids) at the weeks 4, 8 and 12 visits during Phase 3 as compared to the last visit in Phase 2.
- Product satisfaction (Product Evaluation Scale if they used the product since the last visit; Cigarette Evaluation Scale if they smoked cigarettes since the last visit).
- Perceived health risk (Phase 1, Phase 2 and end of week 12 of Phase 3: all products for all subjects).
- Measures of discomfort/dysfunction: MNWS, QSU, CES-D, (NNC vs VLNC cigarettes irrespective of use of products).
- Dependence (FTND, WISDM, PATH items, monthly for study cigarettes)

16.5.4. Safety Endpoints

- Potential adverse consequences: Change in mental (CES-D) or physical health (heart rate, blood pressure, weight).
- Increased TNE (corrected by creatinine), calculated as change from Phase 1 baseline.
- Adverse events and Serious Adverse Events

16.6. Statistical Analysis

16.6.1. General Approach

All statistical analyses will be performed using SAS or R. All statistical tests will be two-tailed. A Bonferroni multiple-comparisons adjustment will be used to account for multiple comparisons for each of the two primary endpoints ($\alpha = 0.025$). Analyses of the secondary and exploratory endpoints will not be adjusted for multiple comparisons ($\alpha = 0.05$). All analyses will be completed using the intent-to-treat principle unless otherwise noted. Methods for handling missing data will be specified below.

16.6.2. Describing the Study Population

Descriptive statistics will be performed for data collected at different visits. Daily Interactive Voice Response (IVR)-Revised data will be summarized by phase and by visit (according to the actual visit dates or scheduled visit dates if a visit is missed). Baseline data will be compared between the two studied conditions with t test or Wilcoxon rank sum test for continuous variables and chi-square test or Fisher's exact test for categorical variables, which include sex, age, race, education, menthol status, dependence (FTND), CPD, nicotine metabolite ratio (NMR) and TNE. Baseline CPD and TNE are based on Phase 2.

16.6.3. Primary Endpoint Analysis

The primary endpoints are (1) the mean cigarettes (study and non-study cigarettes) smoked per day based on 7 days' Daily Interactive Voice Response (IVR)-Revised data before the week 12 visit; and (2) the number of smoke-free days out of the total number of days in Phase 3.

Primary Analysis

We expect the two groups to, on average, be balanced for important baseline characteristics due to randomization, so the primary analyses will be regressions for the difference in CPD and the number of smoke-free days between two conditions, adjusting for only the baseline value (the mean CPD and the percent of smoke-free days during Phase 2, respectively). Specifically, for the CPD outcome at week 12, we will use linear regression; for the number of smoke-free days, we will use Poisson regression or negative binomial regression when there is over-dispersion in the count data.

Secondary Analysis

For the Week 12 CPD and total number of smoke-free days, we will perform an adjusted analysis, adjusting for baseline value, study site (the randomization stratification factor), whether the Week 12 visit is pre-COVID or not, and any baseline characteristics (listed in Section 16.6.2), which are different at $p<0.20$, in multivariable regressions to improve efficiency.

For the CPD outcome measured repeatedly, we will use linear mixed effects models.⁶¹ Fixed effects in the model will include: treatment group, visit, treatment group by visit interaction, baseline CPD, study site, whether the visit time is pre-COVID or not (as a time-dependent covariate), and any baseline characteristics (listed in Section 16.6.2) which are different at $p>0.20$. A random intercept for each subject will also be included in the model to account for within subject correlation.

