16.6.5. Exploratory Endpoint Analysis

We will conduct the following exploratory endpoint analysis:

- For the number of days of non-combusted tobacco/nicotine products use, we will use Poisson or negative binomial regression, adjusting for baseline value, study site, whether the visit is pre-COVID or not, and any baseline characteristics which are different at $p<0.20$.
- Descriptively examine the characteristics of the various products that are chosen (type, nicotine strength, flavor).
- Other biomarkers will be analyzed similar to the Secondary Endpoint analysis.
- Product satisfaction (Product Evaluation Scale, Cigarette Evaluation Scale) at the first time a participant tried a product will be summarized using mean and standard deviation and compared between two treatment arms using linear regression.
- Repeated measure of perceived health risk will be analyzed using the mixed effects model as described in the Secondary Analysis Section.
- Discomfort as assessed by MNWS-R, QSU, and CES-D will be compared between the VLNC vs. NNC cigarette conditions. The methods for comparing discomfort measures between VLNC and NNC cigarettes will be the same as for those described for the Primary Endpoints.
- Repeated measures of dependence of study cigarettes will be analyzed using mixed effects model described in the Secondary Analysis Section.
- Examine the cross-sectional associations of non-combusted products use with cigarettes smoked and biomarkers at different visits using marginal generalized estimating equations (GEE) model⁶² (Chapter 12) with the non-combusted product use as the independent variable.
- We will explore baseline predictors of responses. We will use multivariable regressions to determine predictors of product use patterns, e.g., non-combusted product use, combusted product use, and smoke-free days. Predictor variables (depending on the responses measured) will include baseline CPD, total nicotine equivalents, FTND, age, sex, racial ethnic group, SES, perceived risk of products, product expectancy, product utility, social and environmental influences, contemplation ladder, menthol cigarette use and nicotine metabolite ratio (NMR, reflecting rate of nicotine metabolism). Similar regression models as described in Primary and Secondary Endpoint Analyses will be used.

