6.3.2. Secondary Analysis

For the Week 12 CPD and total number of smoke-free days, we will perform an adjusted analysis, adjusting for baseline value, study site (the randomization stratification factor), whether the Week 12 visit is pre-COVID or not, and any baseline characteristics (listed in Section 6.2) which are different at $p<0.20$, in multivariable regressions to improve efficiency.

For the CPD outcome measured repeatedly, we will use linear mixed effects models (Verbeke and Molenberghs, 2000). Fixed effects in the model will include: treatment group, visit, treatment group by visit interaction, baseline CPD, study site, whether the visit time is pre-COVID or not (as a time-dependent covariate), and any baseline characteristics (listed in Section 6.2) which are different at $p<0.20$. A random intercept for each subject will also be included in the model to account for within subject correlation.

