6.5. Exploratory Endpoint Analysis

- For the number of days of non-combusted tobacco/nicotine products use, we will use Poisson or negative binomial regression, adjusting for baseline value, study site, whether the visit is pre-COVID or not, and any baseline characteristics which are different at $p < 0.20$.
- We will descriptively examine the characteristics of the various products that are chosen (type, nicotine strength, flavor).
- For other biomarkers, similar analyses to Secondary Endpoint will be performed.
- Product satisfaction (Product Evaluation Scale, Cigarette Evaluation Scale) at the first time a participant tried a product will be summarized using mean and standard deviation and compared between two treatment arms using linear regression.
- Repeated measures of perceived health risk will be analyzed using the mixed effects model as described in Section 6.3.2.
- Discomfort as assessed by MNWS-R, QSU, CESD will be compared between the VLNC vs. NNC cigarette conditions. The methods for comparing discomfort measures between VLNC and NNC cigarettes will be the same as for those described for the primary endpoints in Section 6.3.
- Repeated measures of dependence of study cigarettes will be analyzed using mixed effects model described in Section 6.3.2.
- We will examine the cross-sectional associations of non-combusted products use with cigarettes smoked and biomarkers at different visits using marginal generalized estimating equations (GEE) model (Diggle et al, 2002, Chapter 12) with the non-combusted product use as the independent variable.
- We will explore baseline predictors of responses. We will use multivariable regressions to determine predictors of product use patterns, e.g., non-combusted product use, combusted product use, and smoke-free days. Predictor variables (depending on the responses measured) will include baseline CPD, total nicotine equivalents, FTND, age, sex, racial ethnic group, SES, perceived risk of products, product expectancy, product utility, social and environmental influences, contemplation ladder, menthol cigarette use, and nicotine metabolite ratio (NMR, reflecting rate of nicotine metabolism). Similar regression models as described in Sections 6.3 and 6.4 will be used.

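### The protocol reverses the SAP's covariate rule (p>0.20 instead of p<0.20) in the repeated-CPD and CEMA mixed models: a minor sign slip to correct

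*Combined protocol and SAP*

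**What the plan says.** **The conflicting rule.** In Protocol 16.6.3 the mixed model for repeated CPD adds "any baseline characteristics (listed in Section 16.6.2) which are different at $p>0.20". Protocol 16.6.4 gives the same rule for the percent change in biomarker at weeks 4, 8 and 12; CEMA is the only biomarker among the secondary endpoints. For the repeated-CPD model, SAP 6.3.2 adds "any baseline characteristics (listed in Section 6.2) which are different at $p<0.20", and SAP 6.4 repeats that rule for the biomarker model.

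**The rule elsewhere.** The paragraph of Protocol 16.6.3 just before the mixed model uses p<0.20 for the adjusted week-12 analyses. Protocol 16.6.5 has "any baseline characteristics which are different at $p<0.20" for the days-of-use count model, and SAP 6.5 has "any baseline characteristics which are different at $p < 0.20".

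**Candidates.** Protocol 16.6.2 lists nine: "sex, age, race, education, menthol status, dependence (FTND), CPD, nicotine metabolite ratio (NMR) and TNE". Baseline CPD is already a fixed term in the repeated-CPD model, which leaves eight to be screened there.

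**Reuse.** Protocol 16.6.5 states "Other biomarkers will be analyzed similar to the Secondary Endpoint analysis" and "Repeated measures of dependence of study cigarettes will be analyzed using mixed effects model described in the Secondary Analysis Section". It treats perceived health risk in the same way.

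**Precedence.** Protocol 16.1 says "For complete statistical detail, please see Statistical Analysis Plan". Neither document says which text prevails if the two conflict.

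**Site.** Randomisation is stratified by site only (Protocol 16.2, SAP 3.1). The primary models adjust only for the baseline value of the outcome (Protocol 16.6.3, SAP 6.3.1). Site enters the adjusted secondary analysis of both primary endpoints.

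**The concern.** The two rules are exact complements. For any screened characteristic, whatever one document puts in the model the other leaves out.

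The direction matters too. A rule that keeps only covariates with p>0.20 drops those that happen to be imbalanced. The balanced ones that stay reduce the residual variance, so the standard error shrinks, while the chance imbalance in the omitted ones still feeds into the treatment estimate. If those covariates are prognostic, the reported standard error is too small and the test rejects too often. The p<0.20 rule errs the other way and is slightly conservative.

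CEMA is a named secondary endpoint tested at an unadjusted 0.05 (Protocol 16.6.1), and the trial is open label. Its covariate set should not be left to a choice between two texts.

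**Working it through.** **1. The plan's own figures.** Inputs: 400 or 450 enrolled with 20% attrition, so 160 or 180 per arm; CPD difference 15 − 7 = 8, SD 9.62; control smoke-free rate 0.0504, difference 11/84 = 0.131; two-sided alpha 0.025 (z = 2.2414). Sources: Protocol 16.3, SAP 3.2.2 and 3.2.3.

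- CPD, N=400: SE = 9.62 × √(2/160) = 1.076; 8/1.076 = 7.44, well beyond 2.24. Power >.99, as stated.
- Smoke-free days, N=400: SE = √((0.0504 + 0.1814)/160) = 0.0381; 0.131/0.0381 − 2.2414 = 1.20, power 0.885 (stated .88). N=450 gives 0.920 (stated .92).

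These are unadjusted tests, so the covariate rule does not touch them.

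**2. The texts side by side.**

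| Model | Protocol | SAP |
|---|---|---|
| Adjusted week-12 CPD and smoke-free days | p<0.20 (16.6.3) | p<0.20 (6.3.2) |
| Repeated CPD, mixed model | **p>0.20** (16.6.3) | p<0.20 (6.3.2) |
| CEMA, mixed model | **p>0.20** (16.6.4) | p<0.20 (6.4) |
| Days of non-combusted product use | p<0.20 (16.6.5) | p<0.20 (6.5) |

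**3. How many covariates enter by chance.** Under randomisation each baseline p-value falls below 0.20 with probability 0.20.

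- CEMA, nine candidates: 9 × 0.80 = 7.2 under p>0.20; 9 × 0.20 = 1.8 under p<0.20.
- Repeated CPD, eight candidates: 6.4 against 1.6.
- If the nine were independent, the chance that the literal protocol rule drops at least one is 1 − 0.80⁹ = 0.87.

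**4. Type I error at nominal 0.05, by simulation.** Setting: 320 completers (400 × 0.80), 1:1, no treatment effect, least squares on the subject mean, 40,000 runs per cell (Monte Carlo error about 0.001). Simplification: site and COVID terms, and the fixed baseline-CPD term, left out. Assumptions: normal covariates with equal coefficients; dependence, CPD and TNE measures correlated 0.5, the rest independent; joint share of outcome variance (R²) 10, 20 or 30%. The documents give no R².

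| Model | Rule | R² 10% | 20% | 30% |
|---|---|---|---|---|
| Repeated CPD (8) | p>0.20 | 0.056 | 0.062 | 0.070 |
| | p<0.20 | 0.044 | 0.039 | 0.035 |
| | fixed list | 0.050 | 0.049 | 0.051 |
| CEMA (9) | p>0.20 | 0.056 | 0.062 | 0.069 |
| | p<0.20 | 0.047 | 0.041 | 0.037 |
| | fixed list | 0.051 | 0.050 | 0.052 |

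With 360 completers, or with independent covariates, p>0.20 stays within 0.053 to 0.071.

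Smaller runs cover lower R² (Monte Carlo error about 0.002). Nine correlated candidates gave 0.050 at 2% and 0.051 at 5%. Independent covariates gave about 0.051 to 0.058 over 2 to 5%. With baseline CPD kept in the repeated-CPD model, p>0.20 gave 0.055, 0.053 and 0.061 at R² of 5, 10 and 20%.

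**5. Site in the primary CPD model.** If site explains a share s of CPD variance (assumption), leaving it out gives a true size of 2 × [1 − Φ(2.2414/√(1−s))], and adding it gives SE = 1.076 × √(1−s). Both ignore the baseline-CPD term, which would absorb part of any site effect.

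| s | Size without site (nominal 0.025) | SE with site |
|---|---|---|
| 2% | 0.0236 | 1.065 |
| 5% | 0.0215 | 1.048 |
| 10% | 0.0181 | 1.020 |

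Power at a difference of 8 is >.99 in every row.

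**The case against.** The strongest reply is that the documents largely resolve the slip themselves. A characteristic that differs at p>0.20 is nearly a contradiction in terms. The paragraph just before it uses p<0.20 for the same purpose, Protocol 16.6.4 says its methods are similar to that section's, the SAP is consistent throughout, and Protocol 16.1 sends the reader to the SAP. The harm also needs an analyst to carry out an evident misprint, and covariates that explain a sizeable share of variance beyond what is already in the model. CEMA is analysed as a change from Phase 2, and repeated CPD is already adjusted for baseline CPD, so the remaining R² could be small.

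Most of this stands, and it is why the point is minor. It does not remove the contradiction, which is in operative text in two separate sections.

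A reader might go further than the documents allow in four ways:

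- **That type I error is inflated outright.** It is so only if the literal rule is run and the covariates explain roughly 10% or more.
- **That the later date makes p>0.20 govern.** The last protocol revision (11/23/22) follows the last SAP modification (11/21/2022) by two days, but no text makes date decisive and Protocol 16.1 points the other way.
- **That omitting site from the primary models is an error.** Omission makes the linear CPD test mildly conservative, and site is already in the prespecified adjusted analysis.
- **That a site term in the smoke-free-days model can be judged on power.** That depends on a dispersion the documents do not give, so no claim is made.

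**Conclusion.** The contradiction is real and minor. Protocol 16.6.3 (repeated CPD) and 16.6.4 (CEMA) state the reverse of the SAP rule, and p<0.20 is the evident intent. Run literally, the protocol rule would give a type I error of about 0.055 to 0.07 at nominal 0.05 if the covariates explain 10 to 30% of outcome variance, somewhat less for repeated CPD once its baseline term is counted. At 2 to 5% the excess is close to simulation noise. Those variance shares are assumptions.

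The reach is one secondary endpoint, the repeated-CPD analysis, and the exploratory models for other biomarkers, perceived health risk and dependence that refer back to them. Neither primary test is affected. The site remark is a possible refinement for CPD only.

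**What to change.** **Needed.** In Protocol 16.6.3 (repeated-CPD mixed model) and Protocol 16.6.4 (biomarker mixed model), change p>0.20 to p<0.20 to match SAP 6.3.2 and 6.4. The cost is one character in each section and no new data. A general sentence giving the SAP precedence is not needed once the signs agree. It would also be risky, because SAP section 3 still describes 700 subjects from 3 sites while the protocol has 400-450 from six.

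**Optional.** In both documents, replace the p-value screen with the nine characteristics in Protocol 16.6.2, entered whatever their baseline p-values. This holds the nominal level (0.050 to 0.052 at R² of 10 and 30% for CEMA and repeated CPD above, 0.049 to 0.050 at 20%) and removes a data-driven step.

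**Optional, and not a correction.** In Protocol 16.6.3 and SAP 6.3.1, add study site to the primary CPD linear model and keep the baseline-only model as a sensitivity analysis. This uses 5 degrees of freedom for six sites. The trial is open label, enrolment is listed to 9/30/2022 and the SAP was last modified on 11/21/2022, so such a change needs a dated amendment stating that it was made without sight of comparative results. With so small a gain, that is a fair reason to leave it undone. Leave the smoke-free-days primary model as planned; its adjusted secondary analysis already includes site.
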